4.6.1 Primary Efficacy Endpoint

The primary endpoint is the ordinal mRS score at Day 90. mRS is an assessment of disability with values from 0 (no symptoms at all) to 5 (severe disability); death will be scored as a 6. During the study, mRS is collected at Baseline, Day 5 or hospital discharge, and 30 and 90 days after randomization. If death occurs prior to a scheduled assessment day, the mRS will be considered available and will be set to 6. The methodology for imputations related to the primary endpoint is described in Section [4.9.1.1](#).

The distribution of mRS at Day 90 will be summarized descriptively, and plotted using Grotta bars.

Analysis of the primary endpoint will test the hypothesis as follows:

$$H_0: OR_{\{TNK \text{ vs Placebo}\}} = 1 \text{ vs. } H_1: OR_{\{TNK \text{ vs Placebo}\}} \neq 1,$$

where $OR_{\{TNK \text{ vs Placebo}\}}$ stands for the overall odds ratio of achieving a lower level vs. higher level mRS between the tenecteplase and the placebo arms. Superiority of tenecteplase over placebo will be declared if the p-value of the estimated treatment effect is ≤ 0.003 (two-sided) at the efficacy interim analysis or ≤ 0.049 (two-sided) at the final analysis, after adjustment for one efficacy interim analysis.

In case there are issues with fitting the proportional odds model (such as e.g. a quasi-complete separation), the stratified Wilcoxon-Mann-Whitney Generalized Odds Ratio statistic (WMW GenOR) as described below will be employed. Otherwise, the proportional odds assumption will be tested. For this purpose, a proportional odds model will be fitted for the Day 90 mRS outcome, which will include treatment and adjusting variables. If the p-value for the overall score test of the proportional odds hypothesis is > 0.05 , the proportional odds assumption will be deemed acceptable. The assessment of the proportional odds assumption will be independent of the results from the primary efficacy analysis from the proportional odds model.

If the proportional odds hypothesis is not rejected, the parametric proportional odds model described above will be used to analyze the primary efficacy endpoint. The estimated common odds ratio of a lower mRS score (better outcome) will be presented for treatment (TNK vs. placebo). The corresponding Wald p-value and 95% CI will also be obtained.

If the proportional odds hypothesis is rejected, the stratified WMW GenOR will be computed to compare the odds of having a lower mRS in the treatment group compared to placebo. This method does not require the proportional odds model assumption and is easily interpretable, computationally simple, and allows for confidence intervals to be constructed (Churilov et al. 2014). See details in [Appendix 4](#).

An unadjusted analysis of mRS distributions by treatment group will also be performed using the Wilcoxon-Mann-Whitney test (PROC NPAR1WAY) as supportive analysis.

4.6.2 Secondary Efficacy Endpoints

Secondary endpoints will be compared between the two treatment groups, gated on the success of the primary efficacy comparison (2-sided p-value ≤ 0.003 at the interim analysis or ≤ 0.049 at the final analysis). Hypothesis testing of the key secondary endpoints will be performed in a sequential manner at the 2-sided significance level of 0.049 (or 0.003 for interim analysis), the amount available after testing the hypothesis for the primary endpoint. The order of testing is presented in the following table and testing will continue according to this order until the p-value of the hypothesis being tested is > 0.049 (or > 0.003 for interim analysis).

Table 3 Order of Hypothesis Testing for the Secondary Endpoints

Order	Endpoint
1	Proportion of patients with functional independence
2	Proportion of patients with recanalization at 24 hours post-randomization
3	Proportion of patients with reperfusion at 24 hours post-randomization
4	Proportion of patients with angiographic reperfusion (TICI 2b or TICI 3) at completion of angiographic procedure
5	Median NIHSS score at Day 90
6	Proportion of patients with a BI score of ≥ 95 at Day 90
7	Proportion of patients with good recovery based on the Glasgow Outcome Scale at Day 90

BI = Barthel Index; TICI = Thrombolysis in Cerebral Infarction.

4.6.2.1 Functional Independence

A patient with functional independence is defined as having an mRS of 0–2 at Day 90. The proportion of patients with functional independence will be analyzed using logistic regression. The model will be adjusted as specified in Section 4.6. Observed counts and percentages for tenecteplase and placebo arms, and model based odds ratio, corresponding Wald 95% CI and p-value will be produced. This analysis will be performed with the same imputations used in the primary analysis (see Section 4.9.1).

4.6.2.2 Recanalization at 24 Hours Post-Randomization

During the follow up CT or MRI, the degree of recanalization will be evaluated by the central reader. Possible outcome includes no recanalization, partial recanalization, or complete recanalization.

The proportion of patients with complete recanalization at 24 hours post-randomization will be analyzed using logistic regression. The model will be adjusted as specified in Section 4.6. Observed counts and percentages for tenecteplase and placebo arms, and model based odds ratio, corresponding Wald 95% CI and p-value will be produced.

4.6.2.3 Reperfusion at 24 Hours Post-Randomization

Time to maximum of the residue function (T_{max}) is one of the measurements used to estimate salvageable tissue after a stroke and is comparable in MRI and CT perfusions (Seker et al., 2017). For this study, reperfusion at 24 hours post-randomization is defined as $>90\%$ reduction in $T_{max}>6$ s lesion volume, compared to the baseline scan.

The proportion of patients with reperfusion at 24 hours post-randomization will be analyzed using logistic regression adjusted as specified in Section 4.6. Observed counts and percentages for tenecteplase and placebo arms, and model based odds ratio, corresponding Wald 95% CI and p-value will be produced.

4.6.2.4 Angiographic Reperfusion

Angiography is a tool that can measure reperfusion, or restoring the flow of blood, after a stroke or heart attack. The Thrombolysis in Cerebral Infarction (TICI) scale is a grading system that is commonly used to measure the response of thrombolytic therapy in ischemic strokes, using angiographic reperfusion (Higashida RT et al, 2003). TICI scores range from grade of 0 (no reperfusion) to grade 3 (complete reperfusion). Grade 2 (partial reperfusion) is further subdivided into 2a and 2b.

In this study, a secondary efficacy endpoint is the proportion of patients with angiographic reperfusion, defined as achieving TICI 2b or TICI 3 at completion of the angiographic procedure. This analysis will be limited to endovascular patients only. Logistic regression will be used to determine the odds of having an angiographic reperfusion, adjusted as specified in Section 4.6. Observed counts and percentages for tenecteplase and placebo arms, and model based odds ratio, corresponding Wald 95% CI and p-value will be produced.

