6.4.2 Secondary Efficacy Endpoints

For the following binary secondary efficacy endpoints, treatment groups will be compared using logistic regression models adjusted by the randomization strata *and baseline mechanical thrombectomy planned status*, as appropriate:

- Proportion of patients with functional independence, defined as an mRS of 0–2 at Day 90 from randomization

- Proportion of patients with angiographic reperfusion (TICI 2b/3 or TICI 3) at completion of angiographic procedure (endovascular patients only)
- Proportion of patients with recanalization at 24 hours post-treatment, defined as complete recanalization on CTA/MRA
- *Proportion of patients with reperfusion at 24 hours post-treatment, defined as >90% reduction in T_{max} >6s lesion volume*
- Proportion of patients with a BI score ≥ 95 at Day 90 from randomization
- *Proportion of patients with good recovery based on the GOS at Day 90 from randomization*

For the following continuous secondary endpoint, treatment groups will be compared using the van Elteren's test, adjusting for the randomization stratification factors:

- Median NIHSS at 24 hours, 72–96 hours, 30 days, and 90 days

Key secondary endpoints will be compared between the two treatment groups, gated on the success of the primary efficacy comparison (2-sided p-value ≤ 0.049). Hypothesis testing of the key secondary endpoints will be performed in a sequential manner at the 2-sided significance level of 0.049. Additional details of the hierarchical testing of the secondary endpoints will be provided in the SAP.

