1	Contrast passes the area of occlusion but fails to opacify the entire cerebral bed distal to the obstruction during angiographic run
2	Partial perfusion wherein the contrast passes the occlusion and opacifies the distal arterial bed but rate of entry or clearance from the bed is slower than non-involved territories 2A: <50% of territory visualized 2B: ≥50% of territory is visualized 2C: Near complete perfusion except for slow flow in a few distal cortical vessels or presence of small distal cortical emboli
3	Complete reperfusion with normal filling

Source: Spiotta et al. 2019.

Reference:

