4.6.3.5 Patients Requiring One Pass with Endovascular Therapy Device

This endpoint will be defined for endovascular patients for whom the mechanical thrombectomy was performed (i.e. the clot was able to be reached) and a final TICI of 2b or 3 was achieved at the completion of the procedure. The number of passes to reach final TICI 2b/3 will be categorized as 1 vs >1, and analyzed using logistic regression, adjusting as specified in Section 4.6 but excluding the planned thrombectomy variable. If multiple mechanical thrombectomies were reported for a subject, only the initial procedure will be used to define this endpoint. Observed counts and percentages for tenecteplase and placebo arms, and model based odds ratio, corresponding Wald 95% CI and p-value will be produced.

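### The protocol's TICI scale has a grade 2C above 2B, but success is listed only as 2b or 3, and neither document says how a 2C is counted

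*SAP*

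**What the plan says.** **The scale.** Protocol Appendix 8 sets out a modified TICI scale with grades 0, 1, 2A, 2B, 2C and 3. The upper three are:
- for the lowest of the three, "2B: ≥50% of territory is visualized"
- for the middle one, "2C: Near complete perfusion except for slow flow in a few distal cortical vessels or presence of small distal cortical emboli"
- for grade 3, "Complete reperfusion with normal filling"

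SAP 4.6.2.4 describes a scale from 0 to 3 in which "Grade 2 (partial reperfusion) is further subdivided into 2a and 2b". It has no 2c. The two documents also cite different sources for the scale: a 2019 paper in Appendix 8 and a 2003 reporting-standards paper in the SAP.

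**The success rule.** SAP 4.6.2.4 has angiographic reperfusion "defined as achieving TICI 2b or TICI 3 at completion of the angiographic procedure", in endovascular patients only. The same two grades are named in the protocol synopsis, protocol Section 2 (Table 3), SAP 2.2.2, SAP Table 3 and the synopsis reproduced as SAP Appendix 1. Protocol 6.4.2 words it differently: "angiographic reperfusion (TICI 2b/3 or TICI 3").

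**Where it is used.** SAP Table 3 puts this endpoint fourth of seven in the sequential testing, ahead of NIHSS, Barthel Index and Glasgow Outcome Scale at Day 90. SAP 4.6.3.5 restricts the one-pass endpoint to patients whose final grade was 2b or 3, and then: "The number of passes to reach final TICI 2b/3 will be categorized as 1 vs >1".

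**The concern.** A binary efficacy endpoint should not reverse as the outcome improves. With Appendix 8 grades and a rule that lists only 2b and 3, it does: at least half the territory filled is a success, near-complete filling is not, and complete filling is again a success. 2C is the only grade better than a listed success grade that is not itself listed, and no passage says how a recorded 2C is classified.

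The endpoint belongs to the confirmatory sequence. If the primary comparison and the first three secondary tests succeed, the coding of 2C can affect the fourth test and whether the last three are formally reached. Left open, it becomes a choice made in programming, possibly after unblinding.

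**Working it through.** The plan states no rate, sample size or power for the TICI endpoint, so there is no figure to reproduce. The check compares the two definitions and then follows the consequence algebraically.

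**Step 1. Each grade under each reading.** The SAP does not describe 2b in words. I assume that filling which is near complete but not complete falls in the upper part of its grade 2.

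| Appendix 8 grade | Listed as success (2b or 3) | Grade on the SAP's scale | Success on that scale |
|---|---|---|---|
| 0, 1, 2A | no | 0, 1, 2a | no |
| 2B | yes | 2b | yes |
| 2C | **not listed** | 2b | yes |
| 3 | yes | 3 | yes |

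The rule is monotone on the SAP's scale and not monotone on the protocol's.

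**Step 2. Effect on the endpoint if 2C is recorded and not counted.** Let c be the share of an arm's endovascular patients graded 2C.
- Rate in each arm: literal rate = (2b-or-better rate) − c.
- Treatment difference: literal difference = (2b-or-better difference) − (c in tenecteplase − c in placebo).

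So both arms are understated by their own 2C share. The risk difference is distorted only to the extent that the 2C shares differ between arms.

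**Step 3. Illustration.** Every share below is an assumption; none comes from the documents. Shares are percentages in grades 2b / 2c / 3, and odds ratios are unadjusted.

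| Case | Placebo | Tenecteplase | 2b or better | OR | 2b or 3 only | OR |
|---|---|---|---|---|---|---|
| A: 2c equal in both arms | 45/10/20 | 45/10/27 | 75 vs 82 | 1.52 | 65 vs 72 | 1.38 |
| B: part of the gain in 2c | 30/25/20 | 27/30/25 | 75 vs 82 | 1.52 | 50 vs 52 | 1.08 |
| C: whole gain in 2c | 30/25/20 | 30/32/20 | 75 vs 82 | 1.52 | 50 vs 50 | 1.00 |
| D: 5 points move from 2b to 2c | 30/25/20 | 25/30/20 | 75 vs 75 | 1.00 | 50 vs 45 | 0.82 |

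Examples of the arithmetic:
- 2b or better in A to C: (0.82/0.18)/(0.75/0.25) = 1.52.
- Case B, literal: (0.52/0.48)/(0.50/0.50) = 1.08.
- Case D, literal: (0.45/0.55)/(0.50/0.50) = 0.82.

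The differences agree with Step 2: 7 − 0 = 7, 7 − 5 = 2, 7 − 7 = 0 and 0 − 5 = −5 points.

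**Step 4. One-pass endpoint.** Here the final grade decides who is analysed, and the outcome is one pass against more than one. On the literal reading a 2C patient is left out of the analysis set, whatever the number of passes.

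**The case against.** The strongest reply is that the SAP is coherent on its own terms. On its scale near-complete filling is a 2b, hence a success, and the endpoint behaves properly. Several points support this:
- Appendix 8's wording for 2B has no upper limit, so a 2C angiogram also satisfies it.
- The 2b/3 shorthand in protocol 6.4.2 and SAP 4.6.3.5 can be read as a range that takes in 2c.
- The protocol's endpoint table points to appendices for NIHSS, Barthel Index and Glasgow Outcome Scale but to none for TICI.
- Reading is governed by imaging charters (protocol 7.1, SAP 3.2) that are not among the documents, the case report form for TICI is not shown, and the sample code in SAP Appendix 3 does not cover this endpoint.

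All of that stands, and the intent is probably 2b or better. It makes the misclassification conditional but does not remove the point. Protocol Appendix 7 requires angiographic images for TICI scoring, and Appendix 8 is the only grading table supplied for it. The SAP's success set names two discrete grades. A charter might settle which scale readers use, but it would not correct that list.

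The reply is also right that the reach is limited. The endpoint covers endovascular patients only and is formally tested only after four earlier successes. The primary analysis, sample size and safety analyses are untouched.

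**Conclusion.** The point holds as a conditional defect. The two documents describe different TICI scales, and the stated success rule fits only one of them. If grades follow Appendix 8 and the rule is applied literally, near-complete reperfusion is scored as failure in the fourth secondary endpoint and dropped from the one-pass analysis. If grades follow the SAP's scale, neither happens. The documents do not say which applies.

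The size cannot be derived, because no TICI grade frequencies are given. What can be said is structural: each arm is understated by its own 2C share, and a shift from 2b to 2c caused by the drug counts against tenecteplase.

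A reader might infer three stronger things that the documents do not support:
- *That 2C patients will be scored as failures.* This needs 2C to be a recorded category and the program to test for exactly 2b and 3. Neither is stated.
- *That the endpoint would show harm.* This needs a particular movement from 2b to 2c, as in case D. With equal 2C shares (case A) the direction is kept.
- *That the one-pass endpoint also counts 2C as failure.* There the patients are excluded, which is a different error.

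**What to change.** Before unblinding:
1. Name one TICI scale, with the same grades, in both documents and refer to it wherever the endpoint is defined.
2. Define success as 2b or better (2b, 2c or 3) in every place that carries the rule: the protocol synopsis, protocol Section 2 (Table 3) and protocol 6.4.2; and SAP 2.2.2, SAP Table 3, SAP 4.6.2.4, SAP 4.6.3.5 and the synopsis in SAP Appendix 1. Changing only some of these would create a new contradiction.
3. Check that the imaging charters and the case report form use the same scale.

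The cost is a wording change. If 2C is already recorded, or if it is folded into 2b, no new data are needed; the documents do not show which is the case.

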4.6.2.5 National Institutes of Health Stroke Scale

National Institutes of Health Stroke Scale is a questionnaire tool used to quantify the impairment caused by stroke. Scores are calculated by summing the responses on the survey, with higher values indicative of a more severe stroke. Missing responses will not be imputed and will result in a missing total NIHSS score. The range for the score is 0 to 42.

For this study, the NIHSS will be conducted at baseline, 24 hours, 72-96 hours, discharge or Day 5, 30 days, and 90 days. It will also be collected at the time of unscheduled imaging to support determination of sICH. All NIHSS scores will be allocated to analysis windows, and a single value per window will be selected for analysis according to the rules in Section 4.6. NIHSS score at Day 90 is a secondary endpoint.

NIHSS scores at each planned post-baseline time point will be summarized descriptively (mean, median, etc.). The van Elteren's test will be used to compare the distribution of tenecteplase and placebo arms, adjusting as specified in Section 4.6. The median treatment differences will be presented with 95% CI based on the Hodges-Lehmann approach for the location shift (median treatment difference).

4.6.2.6 Barthel Index Score

The Barthel Index is an ordinal scale used to measure performance in activities of daily living (ADL). This 10-item scale describes ADL and mobility (e.g., feeding, bathing, grooming, dressing, bowel control, bladder control, toileting, chair transfer, ambulation, and stair climbing). Each performance item is rated on this scale with a given number of points assigned to each level or ranking. BI scoring ranges from 0 to 100, and lower scores representing greater dependency.

The proportion of patients with a BI score ≥ 95 at Day 90 will be analyzed using logistic regression adjusted as specified in Section 4.6. Observed counts and percentages for

tenecteplase and placebo arms, and model based odds ratio, corresponding Wald 95% CI and p-value will be produced.

4.6.2.7 Glasgow Outcome Scale

The GOS is a scale used to assess recovery of patients with brain damage. The scale has 5 categories, with scale ranging from 1 (death) to 5 (good recovery). For the purpose of analysis, the scale will be reversed so that 1=good recovery and 5=death, to align with the common practice in clinical trials.

If death occurs prior to Day 90, GOS will be considered available and will be set to 5.

The proportion of patients with good recovery, i.e., rescaled GOS score = 1, at Day 90 will be analyzed using logistic regression adjusted as specified in Section 4.6. Observed counts and percentages for tenecteplase and placebo arms, and model based odds ratio, corresponding Wald 95% CI and p-value will be produced.

4.6.3 Exploratory Efficacy Endpoints

4.6.3.1 Subgroup Analyses for the Primary Endpoint

The primary efficacy endpoint, mRS score at Day 90, will be analyzed by the following subgroups: (1) Occlusion type (ICA/M1 or M2 occlusions) and (2) Randomization site (ECC or nECC). These subgroup analyses will be conducted using the same imputations and analysis methodology as the primary endpoint (see Section 4.6.1), however there will be no adjustment by the variable defining the subgroup. Proportionality of odds will not be re-evaluated for each subgroup. mRS score at Day 30 will be analyzed in a similar manner for the randomization site subgroups (ECC or nECC). Additional subgroup analyses for the primary efficacy endpoint are described in Section 4.6.5.

4.6.3.2 Final Infarct Volumes and Infarct Growth

Two follow-up imaging scans will be obtained after randomization, one at 24±6 hours and one at 72-96 hours (or discharge if patient is being discharged prior to 72-96 hours visit) after study drug administration. The scan at 72-96 hours visit (or discharge if patient is being discharged prior to 72-96 hours visit) will be used to evaluate the final infarct volume (captured as infarct volume on CT scan page and diffusion-weighted imaging (DWI) lesion volume on MRI scan page). Infarct growth will be defined as change from baseline at 72-96 hours visit (or discharge if patient is being discharged prior to 72-96 hours visit) in infarct volume. Patient who died before 72-96 hours visit and were not discharged prior to death will be excluded from the analysis.

Final infarct volumes and infarct growth at 72-96 hours visit assessment or discharge will be summarized descriptively (mean, median, etc.) and analyzed with nonparametric methods. The van Elteren's test will be used to produce p-values for the comparison of the distribution of tenecteplase versus placebo arms, adjusting as specified in Section 4.6. The median treatment differences will be presented with 95% CI based on the Hodges-Lehmann approach for the location shift (median treatment difference).

4.6.3.3 Planned Thrombectomy Not Performed for nECC to ECC Transfers

Some patients who were randomized at an nECC may be transferred to an ECC for endovascular therapy. Occasionally, a planned thrombectomy may not need to be performed on such patient, for example, if symptom improvement was observed prior to the planned thrombectomy. This improvement could occur before, during, or after the transfer of the patient.

The proportion of patients where a planned thrombectomy was not performed for patients randomized at an nECC and transferred to an ECC for endovascular therapy will be summarized by treatment group and analyzed using logistic regression. The model will be adjusted as specified in Section 4.6 but excluding the planned thrombectomy variable. Observed counts and percentages for tenecteplase and placebo arms, and model based odds ratio, corresponding Wald 95% CI and p-value will be produced.

